Non-renal tumor dose escalation scheme: Three participants with non-renal tumors will be treated starting at dose level 2. If no dose-limiting toxicities (DLTs, see definitions in 6.2) are seen, that cohort will move on to the phase II portion of the study. If one DLT occurs at the initial dose level, then 3 more patients will be accrued to that cohort. If no further DLTs occur in those 3 patients treated at the initial dose level, then that cohort will move on to the phase II portion of the study. In the phase II portion, if the efficacy criteria are not met, three more patients will be enrolled at the next dose level. Dose will be escalated to the next dose level (3) for the next three patients. If one DLT, an additional three patients will be enrolled at that current dose level. If two or three DLTs, no dose escalation will occur; if this is at the starting dose level 2, dose will be deescalated to the next lower dose level for the next three patients, down to a minimum of dose level 1. If three patients are treated at dose level 2, three more at dose level 3, and there are still no DLTs, the dose will be held at level 3 for all additional non-renal tumor patients.

Renal tumor dose escalation scheme: Three participants with renal tumors will

be treated starting at dose level 1. If no dose-limiting toxicities (DLTs, see definitions in 6.2) are seen, that cohort will move on to the phase II portion of the study. If one DLT occurs at the initial dose level, then 3 more patients will be accrued to that cohort. If no further DLTs occur in those 3 patients treated at the initial dose level, then that cohort will move on to the phase II portion of the study. In the phase II portion, if the efficacy criteria are not met, three more patients will be enrolled at the next dose level. Dose will be escalated to the next dose level (2) for the next three patients. If one DLT, an additional three patients will be enrolled at that current dose level. If two or three DLTs, no dose escalation will occur; if this is at the starting dose level 1 (the lowest dose level), the study will be terminated. If three patients are treated at dose level 2, three more at dose level 3, and there are still no DLTs, the dose will be held at level 3.

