6.1.2.6 Dose-escalation (please refer to Dose Schema section 6.1.2.5): The Phase I and Phase II portions will be done sequentially. If a dose level does not meet the safety criteria (none of three or no more than one out of six develops a DLT), and the next lower dose level does not meet the Phase II pre-specified criteria for efficacy, the study will be terminated. If two or more DLTs are observed at the starting dose level, the SBRT dose will be de-escalated to the next lower dose level; if this happens at dose level 1 (the lowest dose level), the study will be terminated.

The same Phase I/II design applies to both cohorts, Wilms and sarcoma patients, separately, except for the starting dose level in the Phase I portion. There are 3 dose levels (8, 10 and 12 Gy x 3) in this study. Patients with Wilms tumor or other renal tumors will start at dose level 1 (8 Gy x 3) and dose escalation will stop for this cohort at dose level 3 (12 Gy x 3). Ewing sarcoma and rhabdomyosarcoma patients will start at dose level 2 (10 Gy x 3).

6.1.2.7 Stopping rules: If two or more DLTs are observed at the starting dose level, the SBRT dose will be de-escalated to ther next lower dose level; if this happens at dose 1 (the lowest dose level), the study will be terminated.

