11 STATISTICAL CONSIDERATIONS

11.1 Study Design/Endpoints

A 3+3 study design will be used in the Phase I portion and patients will enter the study in sets of three for each cohort. For a given dose level, if none of three patients experiences a DLT, this dose level will move forward to the Phase II portion. However, if one patient experiences a DLT among the first three patients at any dose level, three more patients will be treated at that dose level. The dose level will enter the Phase II portion if no further DLT is observed following observation period of 6 months from treatment completion of third patient in the cohort. If a DLT is observed in any of the three additional patients, this dose level will not move forward to the Phase II portion and the dose will be de-escalated to the next lower level. If two or more patients experience a DLT among the first 3 patients, dose de-escalation will ensue, if applicable, without further testing of that dose level in the phase II portion. The table below shows the probability of entering the phase II portion for a dose level under different true DLT rates.

True DLT rate	5%	10%	15%	20%	30%	40%
Probability of entering phase II	0.97	0.91	0.81	0.71	0.49	0.31

Once a dose level enters the Phase II portion, a two-stage design will be used to evaluate efficacy. The first stage will accrue seven patients, including the patients enrolled at the same dose level in the Phase I portion. If at least two responses are observed among the seven patients, additional eight patients will be entered. If five or more responses are observed among the fifteen patients, there will be no further dose escalation and this dose level will be considered tolerable and effective for this patient population. With this design, the Phase II portion has 90% power to test the response rate of 50% vs. 20% based on a 0.14 level one-sided exact binomial test. The probability of stopping early is 0.58 if the true response rate is 20%; whereas if the true response rate is 50%, this probability is 0.06.

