If a dose level examined in the Phase II portion does not meet the pre-specified criteria for efficacy, the next higher dose level will start in the Phase I portion until a dose level that meets both Phase I and Phase II criteria for safety and efficacy is found. If a dose level does not meet the safety criteria (none of three or no more than one out of six develops a DLT), and the next lower dose level does not meet the Phase II pre-specified criteria for efficacy, the study will be terminated. If two or more DLTs are observed at the starting dose level, the SBRT dose will be de-escalated to the next lower dose level; if this happens at dose level 1 (the lowest dose level), the study will be terminated. The same Phase I/II design applies to both cohorts, renal tumor (cohort 1) and Ewing patients (cohort 2), separately, except for the starting dose level in the Phase I portion.

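### Efficacy failure opens the next higher dose without a clear condition on Phase II DLTs, and without waiting for the 6-month DLT window to close

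*Combined protocol and SAP*

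**What the plan says.** **Trigger for escalation.** In section 11.1, a level that "does not meet the pre-specified criteria for efficacy, the next higher dose level will start in the Phase I portion". Section 6.1.2.5 has the same branch in both cohort schemes: "In the phase II portion, if the efficacy criteria are not met, three more patients will be enrolled at the next dose level". Neither sentence mentions DLTs.

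**DLT rules that might limit it.**
- Section 6.1.2.5: "If two or three DLTs, no dose escalation will occur". This follows the instruction to add three patients after one DLT. Section 11.1 words the counterpart as "If two or more patients experience a DLT among the first 3 patients".
- Section 6.1.2.7: "Stopping rules: If two or more DLTs are observed at the starting dose level", the dose goes down a level, or the study ends if this happens at level 1. Section 11.1 repeats the rule. No phase and no denominator are given.
- Sections 6.1.2.6 and 11.1 define the safety criterion as "none of three or no more than one out of six develops a DLT". They end the study if a level fails it and the next lower level has failed efficacy.

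**Timing.** Section 6.2 counts DLTs up to 6 months after radiotherapy. The stated observation period governs entry to Phase II at the same dose: "The dose level will enter the Phase II portion if no further DLT is observed following observation period of 6 months". Efficacy is disease control at 6 weeks (sections 9 and 11.3), decided at 7 or 15 patients (section 11.1).

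**Range of doses.** The renal cohort starts at level 1, and "dose escalation will stop for this cohort at dose level 3 (12 Gy x 3"). The non-renal cohort starts at level 2. The possible upward steps are therefore renal 1 to 2, renal 2 to 3 and non-renal 2 to 3.

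**The concern.** The trial seeks the lowest dose that is both acceptably safe and active. A level can pass a screen of three or six patients, show more DLTs among the patients added in Phase II, and then fail on efficacy. The efficacy branch, followed literally, then sends children to a higher dose per fraction, and no stated rule clearly prevents it.

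Timing adds to this. The plan describes a 6-month observation period before more patients are treated at the same dose, but states none before patients are treated at a higher one. The decision can be taken at the last patient's 6-week scan, with most of that patient's DLT window still to run.

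**Working it through.** **1. Which rule covers which step**

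| Upward step | Starting-level rule (6.1.2.7) | No-escalation rule (6.1.2.5) | Safety criterion |
|---|---|---|---|
| Renal 1 to 2 | Can be read to apply; precedence not stated | Reads as a 3+3 rule for a set of three | No limit beyond six patients |
| Non-renal 2 to 3 | Can be read to apply; precedence not stated | Same | Same |
| Renal 2 to 3 | Cannot apply: level 2 is not a starting level | Same | Same |

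**2. The plan's own figures reproduce.** With true DLT rate d, the chance of entering Phase II is (1−d)³ + 3d(1−d)⁵. At d = 5, 10, 15, 20, 30 and 40% this gives 0.973, 0.906, 0.814, 0.709, 0.494 and 0.309, matching the table in section 11.1. The two-stage rule (continue at 2 or more of 7, succeed at 5 or more of 15) gives a type I error of 0.141, power of 0.903, and early stopping of 0.577 at 20% and 0.0625 at 50%. All agree with the plan.

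**3. Efficacy failure.** With control rate p, failure is A = P(at most 1 of 7) plus B = P(at least 2 of 7 but at most 4 of 15).

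| p | A | B | A + B |
|---|---|---|---|
| 20% | 0.577 | 0.282 | 0.859 |
| 50% | 0.0625 | 0.0344 | 0.0969 |
| 70% | 0.0038 | 0.0004 | 0.0042 |

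**4. Passing Phase I and having two or more DLTs by patient N.** J(N) = (1−d)³·P[Bin(N−3, d) ≥ 2] + 3d(1−d)⁵·P[Bin(N−6, d) ≥ 1].
- d = 10%: J(7) = 0.0558, J(15) = 0.357
- d = 30%: J(7) = 0.165, J(15) = 0.459

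**5. Joint probability of escalating with two or more DLTs** = A·J(7) + B·J(15). Assumptions: DLT and response are independent, and no DLT rule acts in Phase II. The DLT rates are also assumed. The 10% rate is about the highest adult grade 3 or worse rate in the section 1.2 table (10.1%); 30% is an unfavourable case.

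| DLT rate | Control | Calculation | Joint |
|---|---|---|---|
| 30% | 20% | 0.577×0.165 + 0.282×0.459 | 0.22 |
| 10% | 20% | 0.577×0.0558 + 0.282×0.357 | 0.13 |
| 30% | 50% | 0.0625×0.165 + 0.0344×0.459 | 0.026 |
| 10% | 50% | 0.0625×0.0558 + 0.0344×0.357 | 0.016 |
| 30% | 70% | 0.0038×0.165 + 0.0004×0.459 | 0.0008 |

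**6. Renal 2 to 3, counted from the start of level 1.** Assume 10% DLT at level 1, 30% at level 2, and equal control at both. Multiply the chance that level 1 passes and escalates by the joint figure for level 2.
- At 20% control: (0.906×0.859 = 0.778) × 0.2245 = 0.17
- At 50% control: (0.906×0.0969 = 0.0878) × 0.0261 = 0.002

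If the starting-level rule does stop level 1 at two DLTs, the 20% figure becomes (0.778 − 0.133) × 0.2245 = 0.145.

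**7. Waiting period.** Six weeks is 6/4.345 = 1.38 months, so 6 − 1.38 = 4.62 months of the window remain. If DLT times were uniform over 6 months (assumed), the last patient's chance of a DLT after the scan is d×4.62/6: 7.7% at d = 10% and 23% at d = 30%. At the accrual in section 11.2, the gap spans 3×4.62/12 = 1.2 renal or 5×4.62/12 = 1.9 non-renal enrolments.

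**The case against.** **Rules do exist.** Section 6.1.2.7 is headed as a stopping rule and is not limited to Phase I. The natural, safe reading is that it overrides escalation. That would settle two of the three upward steps, leaving only a drafting ambiguity about precedence. A reader might infer that nothing restrains escalation after Phase II toxicity; the documents do not support that. What stands is that precedence is unstated and that this rule cannot reach renal level 2.

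**Renal 2 to 3 is not empty.** The no-escalation sentence in section 6.1.2.5 comes after the efficacy branch and is not tied to the starting level, and the termination clause could be stretched to level 2. But the first reads as part of the 3+3 sequence, and the second rests on a criterion that ends at six patients. The gap is one of clarity, and it is real.

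**The size depends on low control.** Control counts stable disease, progression needs both a 20% and a 5 mm increase, new lesions are ignored, and the reading is at 6 weeks (sections 9 and 9.1). Adult local control in section 1.2 is 86–98%, though in another population and generally at higher doses. A reader might take the chance of escalating at all (0.494×0.859 = 0.42 at 30% DLT and 20% control) as the size of the problem. It is not: it includes escalations with no excess of DLTs.

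**The late-DLT figure overstates the effect on decisions.** One late DLT changes the decision only if the earlier count already sits at the limit. With the other patients' windows complete, and using the 1-in-6 limit proposed below, that happens in about 3.0% (7 patients) or 1.9% (15 patients) of cases at a 10% DLT rate, and 14% or 4.6% at 30%.

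**Other safeguards.** A new level restarts 3+3, the DSMC meets quarterly and may receive DLT data (section 12.3), and SAEs within 6 months go to the principal investigator within 24 hours and also to the IRB (section 6.3.2.3.2). A reader might infer that Phase II toxicity goes unwatched; it does not. None of these, however, is a stated rule that stops a higher level from opening.

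**Conclusion.** The concern holds as a gap in the decision rules; the plan's arithmetic is sound. Efficacy failure opens a higher dose without a clear Phase II DLT condition. Precedence is unstated at renal level 1 and non-renal level 2, no rule clearly covers renal 2 to 3, and no step requires the 6-month window to close first.

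The exposure is material mainly when disease control is low: 0.13 to 0.22 at the design's null of 20%, 0.016 to 0.026 at its alternative of 50%, and negligible at 70%. Low control is also the case for which the escalation branch was written. These figures rest on independence of DLT and response, on assumed DLT rates, and on no DLT rule acting in Phase II. If section 6.1.2.7 does act there, the exposure that remains is the renal 2-to-3 step. The plan should be clarified, and confidence is medium because parts of the text allow a safer reading.

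**What to change.** Amend sections 6.1.2.5 and 11.1 to state:

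1. After efficacy failure, a higher level opens only if the current level, counting all its Phase I and Phase II patients, still meets the safety criterion carried forward at the protocol's own proportion of at most 1 in 6. Since 7/6 = 1.17 and 15/6 = 2.5, there is no escalation at 2 or more of 7, or 3 or more of 15. This overrides the efficacy-failure branch.
2. All patients at the current level complete the 6-month DLT window before the higher level opens.
3. The starting-level rule in section 6.1.2.7 stays in force and takes precedence over escalation. It is stricter than item 1 if it covers Phase II, because 2 of 15 would trigger it. Any relaxation is for the sponsor to decide.
4. If the limit is exceeded at renal level 2, the termination rule in section 11.1 applies, because level 1 has already failed efficacy.

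**Cost.** A protocol amendment, and up to about 4.6 months' delay before a higher level opens. At 20% control, the 1-in-6 limit blocks about 2% of escalations at a true DLT rate of 5% and 9% at 10%, against 28% at 20% and 48% at 30%. At the starting levels, reading section 6.1.2.7 to cover Phase II blocks more: 0.133/0.778 = 17% at a 10% DLT rate.

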11.2 Sample Size, Accrual Rate and Study Duration

We expect to accrue 3 patients per year in the renal tumor cohort (cohort 1) and 5 per year in the non-renal (Ewing/RMS) cohort (cohort 2). The maximum total accrual for a given dose level for both cohorts combined is 30. The accrual is expected to be completed in 5

years in the renal cohort and 2 years in the nonrenal cohort, for a dose level to be examined in both the Phase I portion and the Phase II portion.

11.3 Analysis of Primary Endpoints

This is a Phase I/II study to determine the lowest dose level of stereotactic body radiotherapy (SBRT) with an acceptable safety profile and efficacy in patients with relapsed Ewing sarcoma, rhabdomyosarcoma, soft tissue sarcoma or primary renal tumors (including Wilms tumor) who have limited pulmonary metastases. The primary objective of the Phase I portion is to evaluate the toxicity profile of each dose level and determine whether a given dose level could move forward to the Phase II portion. The primary endpoint of the Phase II portion is response to treatment (disease control at 6 weeks in the treatment field). The response rate along with the 95% two-stage confidence interval will be reported by dose level for each cohort. The Phase I and Phase II designs will be employed sequentially, i.e., a dose level will be examined in the Phase I portion for safety and then in the Phase II portion for efficacy if the Phase I safety criteria are met, to achieve the goal of balancing safety and efficacy in these rare tumor populations.

Given that the starting dose in the Phase I portion will be different for the patients with Wilms/renal tumor and the patients with relapsed Ewing sarcoma, rhabdomyosarcoma, soft tissue sarcoma, patients will be enrolled in two distinct cohorts, and escalate through the dose levels and enter the Phase II portion independently.

11.4 Analysis of Secondary Endpoints

Secondary endpoints include relapse elsewhere in the lung and toxicities, and these analyses will be performed by dose level. The method of Kaplan and Meier will be used to characterize time to relapse elsewhere in the lung. All patients who receive any part of the treatment will be monitored for toxicity, and the percent of patients with various toxicities will be tabulated for each dose level. Assuming a total of 15 patients treated at a dose level, if the true probability of a rare toxicity is 5%, the probability of observing 1 or more rare toxicities is 54%. A 90% confidence interval for any toxicity will be no wider than 46%.

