2.3 Secondary Objectives

- 1. To determine the feasibility of SBRT in the pediatric population (including tolerability)
- 2. To document the safety of the treatment
- 3. To determine rate of relapse elsewhere in the lung
- 4. Best overall response

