3. PARTICIPANT SELECTION

3.1 Eligibility Criteria

- 1. Diagnosis of Ewing sarcoma, rhabdomyosarcoma, osteosarcoma, non-rhabdomyosarcoma soft tissue sarcoma, Wilms tumor or other primary renal tumor (including clear cell and rhabdoid)
- 2. Age ≤21 years
- 3. Must be capable of treatment without general anesthesia
- 4. Lesion size 4 mm 3 cm

5. Subjects who have lesions within 2 cm of central structures*, will be eligible on a case-by-case basis

*Tumor within or touching the zone of the proximal bronchial tree, defined as a volume 2 cm in all directions around the proximal bronchial tree (carina, right and left main bronchi, right and left upper lobe bronchi, intermedius bronchus, right middle lobe bronchus, lingular bronchus, right and left lower lobe bronchi).

- 6. Pulmonary metastases found at relapse (does not have to be first relapse); no more than 3 lesions per hemi-thorax will be treated but other lesions in the lung may be present
- 7. Greater than 5 weeks from doxorubicin at the time of consent, with radiation to be initiated no less than 6 weeks from doxorubicin
- 8. Informed consent/assent
- 9. Life expectancy > 3 months
- 10. Pulmonary function FEV₁ ≥ 50% of predicted
- 11. Concurrent immunotherapy is allowed

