9. PARTICIPANT ASSESSMENTS

Evaluation of response. All participants included in the study will be assessed for response to treatment, unless the subject received systemic therapy prior to the 6 week assessment.. Response in this study will be defined as disease control in the treated lesion at 6 weeks. We will continue to assess response and consider best overall response as a secondary objective.

Each participant will be assigned one of the following categories: 1) complete response, 2) partial response, 3) stable disease, 4) progressive disease, 5) early death from malignant disease, 6) early death from toxicity, 7) early death because of other cause, or 9) unknown (not assessable, insufficient data). By arbitrary convention, category 9 usually designates the "unknown" status of any type of data in a clinical database.

Disease control at 6 weeks will include complete response (CR), partial response (PR) and stable disease (SD).

Patients will be seen weekly during treatment for physical examination and assessment of acute side effects. They will then be seen at one month from the end of study treatment for physical examination, A CT at will be done at 6 weeks post completion of SBRT and then every three months with physical examination and CT scan of the chest during the first year, followed by every 6 months for the next year and then annually until year 5, as is considered standard of care. (See: Study Calendar)

The lesion or lesions treated will be measured as well as new lesions identified. Pulmonary function tests will be done at 3 months post treatment, then at 9 months.

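### Section 11.4 plans Kaplan-Meier for lung relapse without saying how death before relapse is handled; if such deaths are censored, the reported relapse rate can be too high but never too low

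*Combined protocol and SAP*

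**What the plan says.** Section 2.3 lists as its third secondary objective "To determine rate of relapse elsewhere in the lung". Section 11.4 makes this an endpoint: "Secondary endpoints include relapse elsewhere in the lung and toxicities, and these analyses will be performed by dose level". The method follows: "The method of Kaplan and Meier will be used to characterize time to relapse elsewhere in the lung".

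Nothing more is specified. The documents give no definition of the event, no time origin and no censoring rule, and they mention neither competing risks nor cumulative incidence. Section 9 has three early-death categories, but they classify response to treatment and are not tied to this endpoint.

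Four other provisions bear on the point:

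- Section 3.1 sets a survival minimum for entry: "Life expectancy > 3 months".
- Section 3.1 lets patients enter with untreated lung disease: "no more than 3 lesions per hemi-thorax will be treated but other lesions in the lung may be present".
- Section 9 schedules chest CT every three months in year 1, "followed by every 6 months for the next year and then annually until year 5".
- Section 11.4 computes its toxicity precision "Assuming a total of 15 patients treated at a dose level".

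**The concern.** The endpoint is relapse alone, not relapse-free survival. Applied to a single event type, Kaplan-Meier normally censors a patient who dies without that event. Censoring treats the patient as still able to relapse later, and redistributes their share of the probability over those still followed. The resulting 1-KM describes relapse in a hypothetical setting without death. It does not estimate the proportion of treated patients who relapse elsewhere in the lung, which is the natural reading of the objective.

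Death is a plausible competing event here. Patients have relapsed metastatic disease, the entry criterion on life expectancy is short, and scans run to year 5. The stake is how well a descriptive secondary result can be read: a published lung-relapse rate could be too high, and its confidence interval would not reflect that error.

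The silence matters too. Censoring death and counting death as an event give different quantities, and the choice could be made after the data are seen.

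**Working it through.** **Is there a figure to reproduce?** The documents state no lung-relapse rate, event count or precision for this endpoint. The neighbouring toxicity figures in section 11.4 do reproduce. The chance of at least one event among 15 patients at 5% is 1 − 0.95^15 = 0.537 (stated 54%). The widest exact 90% interval for n = 15 is 45.6 points (stated no wider than 46%).

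**Inputs.** From the documents: the method, the event (relapse only), n = 15 per dose level and follow-up to year 5. Assumed, because the documents give no values: the relapse hazard r, the hazard d of death without lung relapse, and the event counts used below.

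**Constant hazards.** With deaths censored, 1-KM estimates

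1 − exp(−r·t).

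The proportion of patients who relapse by time t (cumulative incidence, CIF) is

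r/(r+d) × [1 − exp(−(r+d)·t)].

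For r = 0.8 and d = 0.1 at 1 year: 1-KM = 1 − exp(−0.8) = 0.551, and CIF = (0.8/0.9) × [1 − exp(−0.9)] = 0.528. The other rows follow in the same way.

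| r per year | d per year | Year | 1-KM | CIF | Gap (points) |
|---|---|---|---|---|---|
| 0.8 | 0.05 | 1 | 55.1% | 53.9% | 1.2 |
| 0.8 | 0.05 | 2 | 79.8% | 76.9% | 2.9 |
| 0.8 | 0.1 | 1 | 55.1% | 52.8% | 2.3 |
| 0.8 | 0.1 | 2 | 79.8% | 74.2% | 5.6 |
| 0.8 | 0.4 | 1 | 55.1% | 46.6% | 8.5 |
| 0.8 | 0.4 | 2 | 79.8% | 60.6% | 19.2 |

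**By count, at the plan's n = 15.** Take complete follow-up and single events. The cumulative incidence is then relapses/15. Each relapse multiplies the Kaplan-Meier curve by (1 − 1/number still at risk), and each death only lowers the number at risk. The table gives 1-KM averaged over all orderings of relapses and deaths, and at the extreme where every death comes first, when it equals relapses/(15 − deaths).

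| Relapses | Deaths without relapse | CIF | Mean 1-KM | 1-KM, deaths first |
|---|---|---|---|---|
| 5 | 1 | 33.3% | 34.7% | 35.7% |
| 5 | 2 | 33.3% | 36.2% | 38.5% |
| 5 | 5 | 33.3% | 42.2% | 50.0% |
| 8 | 1 | 53.3% | 55.7% | 57.1% |
| 8 | 2 | 53.3% | 58.4% | 61.5% |
| 8 | 5 | 53.3% | 70.6% | 80.0% |

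If no patient dies without relapse, or if every such death follows the last relapse, 1-KM equals the cumulative incidence exactly. With one or two such deaths the average gap runs from 1.4 points (34.7 − 33.3) to 5.1 points (58.4 − 53.3).

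**Against sampling error.** The exact 95% interval has a half-width of 24.9 points for 5 of 15 and 26.1 points for 8 of 15.

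**If death were counted as an event instead.** With 5 relapses and 2 deaths the composite is 7/15 = 46.7%, against 33.3% for relapse alone and a mean of 36.2% for 1-KM. One sentence in section 11.4 therefore leaves room for materially different results.

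**The case against.** The strongest reply is that the plan never says deaths are censored. That is true. Censoring is an inference from how Kaplan-Meier is ordinarily applied to an event that excludes death. The point must therefore stay conditional, although the silence is itself a gap.

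A reader might infer that the relapse rate is bound to be too high because death is frequent in this population. The documents do not support that. The life-expectancy criterion is a minimum for entry, not an expected survival. What matters is death *without* prior lung relapse: every patient has lung metastases and chest CT is frequent in year 1, so many deaths could follow a recorded lung relapse. No rate is given either way, and in the low-hazard rows above the gap is only 1 to 6 points.

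A reader might also infer that comparisons between dose levels would be distorted. No such comparison is planned. Section 11.4 reports results by dose level without a test, and escalation stops once a level is judged effective, so a cohort may have only one level.

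It can also be said that the objective asks for a rate and section 11.4 for time to relapse, so neither commits to the proportion of patients who relapse. That reading is open. But if the hypothetical rate without death is what is wanted, the plan should say so, because most readers will take the curve as the proportion relapsing.

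Finally, with few deaths the bias is small beside sampling error at n = 15. That stands, and it limits the importance of the point. It does not remove it, because the error always runs in the same direction.

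**Conclusion.** The point holds in conditional form. Section 11.4 applies Kaplan-Meier to an event that excludes death and gives no rule for death without lung relapse. If such deaths are censored, 1-KM equals the cumulative incidence or exceeds it, and it exceeds it whenever one of these deaths precedes a later relapse.

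The direction is certain under that condition; the size cannot be found from the documents. Over the assumed hazards it runs from about 1 point to about 19 points by 2 years. For one or two such deaths among 15 patients it averages about 1 to 5 points.

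The consequence is limited. The endpoint is secondary and descriptive, and it enters neither the DLT rule, the 6-week response decision nor the sample size. The change is still worth making, because a method that matches the objective is available at little cost.

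**What to change.** In section 11.4:

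- Report the Aalen-Johansen cumulative incidence of relapse elsewhere in the lung, by dose level with a confidence interval, treating death without lung relapse as a competing event.
- Use Kaplan-Meier only for a composite that counts death as an event, such as survival free of lung relapse.
- State the time origin and the censoring rule for patients alive without relapse.
- State whether growth of untreated lung lesions present at entry counts as relapse elsewhere. Section 3.1 allows such lesions, and changing the estimator alone would leave the event undefined.

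The cost is a few sentences and slightly more analysis work. No extra patients or scans are needed, since section 9 already has new lesions recorded at follow-up. One item needs confirmation: that dates of death are captured through year 5. The study calendar has no survival item and does not mark adverse event reporting for years 3 to 5. Section 6.3.2.3.2 mentions deaths in long-term follow-up only as something to report at continuing review. If death dates are not on the case report form, a field should be added.
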